8.4 Statistical Methods

The planned analyses will include descriptive statistics on the proportions of responses (i.e. % subjects with partial or complete response) and the time to response. The response probabilities will be estimated using the sample proportions and their inferences including confidence intervals and hypotheses testing will be evaluated using Binomial distributions. The time to responses will be analyzed using appropriate tools in survival analysis such as Kaplan-Meier estimates and Cox regression taking consideration of random censoring. In addition methods based on survival analysis, cumulative incidence rates for response and other competing risk models will be used to evaluate the treatment effects. Graphical tools will be used to display the appropriate estimates (i.e. estimated proportions and Kaplan-Meier curves) and their corresponding 95% confidence intervals. Methods based on multiple regression, analysis of variance and logistic regression will also be employed if deemed appropriate.

8.5 Stopping Rules

The following two types of treatment related severe adverse events will be monitored and considered for early stopping for all or part of the study:

- Death considered to be definitely related to alemtuzumab (Campath-1H®)
- Any grade IV toxicity considered to be definitely related to alemtuzumab (Campath-1H®), i.e. opportunistic infection such as tissue-invasive CMV or *Pneumocystis carinii*, with exception of temporary cytopenias.

We will monitor the numbers of subjects who have developed one or more of the above treatment related severe adverse events (TRSAE). The study will be seriously considered for early stopping if the corresponding number of subjects who have developed one or more of the above TRSAE is over a pre-specified threshold value.

From our experience using this agent in other clinical settings, we anticipate the rate of developing at least one of the above TRSAE to be 10% or less. Following Geller et al. (2003, "Design of Early

Trials in Stem Cell Transplantation: A Hybrid Frequentist-Bayesian Approach”), our stopping rule is determined by a Bayesian approach.⁷⁶ The stopping boundary is reached if the Bayesian posterior probability that the true probability of developing one or more of the above TRSAE exceeds this benchmark rate of 10% is at least 90%. We take our prior distribution to be a beta distribution with the sum of the two beta parameters to be 6, i.e. the parameters of the beta prior distribution are 1.0 and 5.0. Since we have seen in the past that the first few subjects to be accrued are possibly sicker than the rest of the subjects in the sample, we will start safety monitoring when 3 or more subjects have developed TRSAE. The following table summarizes the threshold numbers for stopping an experiment:

Number of Subjects in the experiment	Stop if the number of subjects who have developed any of the TRSAE reaches:
≤ 9	3
≤ 16	4
≤ 23	5
≤ 31	6
≤ 38	7
≤ 46	8
≤ 54	9
≤ 62	10
≤ 70	11
≤ 78	12

We investigated the performance of the above stopping rule by a simulation study. In each simulation run, we generated a study with 78 independent Bernoulli trials, each had a probability p for having the above TRSAE and $q=1-p$ for not having such TRSAE and compared the TRSAE outcomes with the above stopping boundary to determine whether the study was stopped. We repeated the simulation 100,000 times and computed the proportion of stopped studies (i.e. “number of stopped studies”/100,000) which were stopped using the above stopping rule. The following table summarizes the proportions of stopped studies under a number of scenarios for p :

Prob of TRSAE = p	2%	5%	10%	15%	20%	25%
Proportion of Stopped Studies	0.7%	1.7%	21.8%	65.4%	92.8%	99.6%
Average Number of Subjects	77.95	76.93	67.32	46.97	28.46	18.17
Average Numbers of Subjects Suffering TRSAE	1.55	3.86	6.73	7.03	5.70	4.55

These results suggest that our stopping rule has a low probability of stopping a study when the proportion of the above TRSAE is below the benchmark value of 10%, and the probability of stopping a study is high when the true proportion of the above TRSAE exceeds this benchmark value. Based on these results, we believe that our Bayesian stopping rule has satisfactory statistical properties.

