8.3 Sample Size

Because the efficacy of this treatment is almost completely unknown, we would like to reject the treatment as quickly as possible with a small number of subjects if the treatment is not effective.

A response probability of 30% or less would warrant terminating the treatment on this subject population, and we hypothesize that the actual response probability using this treatment would reach 50% or more.

Let p be the probability of complete or partial response at 3 months. Our sample size is determined by testing the null hypothesis $H_0: p \leq 30\%$ versus the alternative $H_1: p \geq 50\%$ at 0.05 significance level and 0.80 of the power. We determine the sample size using the Two-Stage Minimax Design outlined in Table 1 of Simon (1989)⁷⁵ This design is selected because it requires a smaller total number of subjects ($n=39$) than the Simon's Two-Stage Optimal Design ($n=46$). At the first stage, 19 subjects will be accrued and the null hypothesis will be accepted (i.e., the treatment will be terminated) if 6 or less subjects respond to the treatment at 3 months. If 7 or more subjects respond to the treatment at 3 months in the first stage, then an additional 20 subjects will be accrued, bringing the total number of subjects to $n=39$. The null hypothesis of $p \leq 30\%$ will be accepted if the total number of complete and partial responders at 3 months is 16 or less.

An additional 39 subjects will be enrolled to allow for statistically valid subgroup comparisons of secondary endpoints such as response to cyclosporine in subjects who relapse within six months of treatment.

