10.4 Risks in Relation to Benefits

For adult subjects:

The potential benefits to the subject include reduction or even abolition of transfusion requirements and/or improvement of cytopenia, resulting in improved quality of life and also decreased morbidity and mortality from transfusion-associated viral agents, iron overload, and/or a susceptibility to infections. For patients with MDS who have failed initial immunosuppression therapy and do not have a histocompatible matched sibling donor, therapeutic options are limited. Although unrelated donor stem cell transplantation has been reported with success, the morbidity

and mortality are still considerably higher than a transplant with a matched sibling donor. Potentially, treatment with other more toxic therapies could also be avoided or postponed.

Therefore, the research involves greater than minimal risk to subjects with the prospect of direct benefit (45 CFR 46.102)

As of January 27, 2017, this study will no longer be in subject follow-up and will continue in data analysis only; the level of risk is now minimal.

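### The safety boundary printed in Section 8.5 does not follow from the stated Beta(1.0, 5.0) prior and 90% posterior rule: at 36 of 76 counts the table requires one more event

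*Combined protocol and SAP*

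**What the plan says.** Section 8.5 (Stopping Rules) specifies the safety rule in full. The monitored event is a death, or a grade IV toxicity other than temporary cytopenia, judged definitely related to alemtuzumab. The boundary is reached when the posterior probability that the true event rate "exceeds this benchmark rate of 10% is at least 90" per cent. The prior is "a beta distribution with the sum of the two beta parameters to be 6", made explicit as "the parameters of the beta prior distribution are 1.0 and 5.0". Monitoring starts once 3 subjects have had an event.

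A threshold table follows, headed "Stop if the number of subjects who have developed any of the TRSAE reaches". It gives 3 events up to n=9, 4 up to 16, 5 up to 23, 6 up to 31, 7 up to 38, 8 up to 46, 9 up to 54, 10 up to 62, 11 up to 70 and 12 up to 78.

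The section then reports 100,000 simulated studies of 78 subjects each, which "compared the TRSAE outcomes with the above stopping boundary". From these it concludes that the Bayesian rule performs satisfactorily.

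**The concern.** A prior, a benchmark, a posterior cut-off and a minimum event count determine one boundary and leave no room for choice. If the table differs from that boundary, the section pre-specifies two safety rules. The operating characteristics that support the design then apply to only one of them.

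Reaching the boundary prompts serious consideration of stopping; it does not stop the study automatically. Section 10.4 adds that from January 2017 "this study will no longer be in subject follow-up and will continue in data analysis only". No future enrolment decision therefore depends on this. What remains at stake is the safety statement in the final report: the same cumulative event count can have reached the boundary under the written rule and not under the table.

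**Working it through.** **Inputs (all Section 8.5).** Prior Beta(1, 5); benchmark 0.10; cut-off 0.90; at least 3 events; maximum 78 subjects; the ten printed row limits.

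**Formula.** With x events in n subjects the posterior is Beta(1+x, 5+n−x). The parameters are whole numbers, so the posterior probability is a binomial tail that can be checked by hand:

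P(rate > 0.10 | x, n) = P(Bin(n+5, 0.10) ≤ x).

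The threshold at each n is the smallest x ≥ 3 for which this is at least 0.90.

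**Worked points.**

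| Events / n | Posterior, Beta(1, 5) | Stated rule | Table |
|---|---|---|---|
| 3 / 10 | P(Bin(15, 0.1) ≤ 3) = 94.4% | reached | needs 4 |
| 3 / 13 | P(Bin(18, 0.1) ≤ 3) = 90.2% | reached | needs 4 |
| 3 / 14 | P(Bin(19, 0.1) ≤ 3) = 88.5% | not reached | needs 4 |
| 4 / 19 | P(Bin(24, 0.1) ≤ 4) = 91.5% | reached | needs 5 |
| 7 / 39 | P(Bin(44, 0.1) ≤ 7) = 93.2% | reached | needs 8 |
| 12 / 78 | P(Bin(83, 0.1) ≤ 12) = 93.1% | reached | reached |

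**Whole boundary: last n for each event count.**

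| Events | 3 | 4 | 5 | 6 | 7 | 8 | 9 | 10 | 11 | 12 |
|---|---|---|---|---|---|---|---|---|---|---|
| Printed table | 9 | 16 | 23 | 31 | 38 | 46 | 54 | 62 | 70 | 78 |
| Beta(1, 5), 90% | 13 | 20 | 27 | 35 | 42 | 50 | 58 | 66 | 74 | 78 (end of study) |

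The first nine limits differ by 4 subjects each, so the versions disagree at 9 × 4 = 36 of the 76 counts from n=3 to n=78. These are n = 10–13, 17–20, 24–27, 32–35, 39–42, 47–50, 55–58, 63–66 and 71–74. At each of them the table requires exactly one more event.

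**Could another reading rescue the table?**
- Using a strict inequality instead of at least 90% leaves the 36 differences unchanged.
- No single cut-off works under Beta(1, 5). The table must not flag 3 in 10 (94.4%) but must flag 12 in 78 (93.1%). On a grid from 0.85 to 0.99 in steps of 0.005 the closest cut-off, 0.93, still misses 5 counts.
- A different prior does work. Beta(1, 9) and Beta(0.5, 5.5), each with the 90% cut-off, reproduce all 76 thresholds. For Beta(1, 9) the reason is algebraic: its posterior at n−4 subjects is identical to that of Beta(1, 5) at n, which explains the constant gap of 4.
- Beta(0.5, 5.5) keeps the stated sum of 6. Beta(1, 9) has sum 10 and mean 10%.

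**Operating characteristics.** These come from exact recursion over 78 Bernoulli outcomes with a look after every subject.

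| True rate p | Stopped: printed | Table, exact | Stated rule, exact | Mean n: printed | Table, exact | Stated rule, exact |
|---|---|---|---|---|---|---|
| 2% | 0.7% | 0.08% | 0.23% | 77.95 | 77.94 | 77.85 |
| 5% | 1.7% | 1.7% | 3.7% | 76.93 | 76.92 | 75.68 |
| 10% | 21.8% | 21.9% | 30.7% | 67.32 | 67.26 | 61.69 |
| 15% | 65.4% | 65.7% | 73.3% | 46.97 | 46.81 | 39.66 |
| 20% | 92.8% | 92.7% | 94.9% | 28.46 | 28.55 | 23.41 |
| 25% | 99.6% | 99.2% | 99.5% | 18.17 | 18.22 | 15.19 |

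The printed values from 5% to 20% reproduce from the table and not from the stated rule. The stopping proportions at 2% and 25% do not reproduce from the table. With 100,000 runs the Monte Carlo standard error for the table is about 0.009 percentage points at 2% and 0.028 at 25%, so chance does not explain either cell. They do not match the stated rule either, although 99.6% lies closer to its 99.5%. The mean sample sizes in those two columns do fit the table.

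**The case against.** The strongest reply is that the table and its simulation form a coherent pair and the sentence naming the prior is the outlier. The table is what staff would use, the simulation was run on it, and four of the six stopping proportions and all the mean sample sizes agree with it. On that view a prior was misdescribed and there were never two live boundaries. Much of this stands, and it makes a misdescribed prior plausible. But Section 8.5 also defines the boundary by the posterior probability, and it gives the parameters both individually and as a sum. At least two other priors generate the table, and the documents do not show which, if either, was used.

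The practical effect is also limited. The versions agree at 40 of 76 counts, including n=78. Section 9.2.4 halts accrual pending discussion with the IRB when a serious adverse event is attributed to the experimental component. Section 9.1 provides DSMB review every 6 to 12 months, and Section 9.2.3 an independent monitor of attribution. These safeguards lower the stakes but do not settle which boundary was pre-specified.

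Finally, changing thresholds after the data are in could look like rewriting the rule. That is a fair caution and a good reason to report against both versions.

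**Conclusion.** The concern holds. The printed boundary is not the one that the stated prior and cut-off produce. It is more permissive by one event at 36 of 76 counts and never stricter. The versions differ at both planned efficacy counts in Section 8.3, where "At the first stage, 19 subjects will be accrued" and the total is then brought to 39: 5 against 4 events at n=19, and 8 against 7 at n=39. Section 8.5 does not tie safety looks to those counts.

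At the 10% benchmark the stated rule would stop 30.7% of studies against 21.9% for the table, a difference of 8.8 percentage points. The claim of satisfactory properties therefore describes the table only. The two inconsistent simulation cells are secondary, and the main finding does not depend on them.

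The boundary comparison uses only figures in Section 8.5. The operating characteristics also assume independent events with a constant rate and a look after each subject; the agreement with most of the printed figures supports that reading. No efficacy estimate or sample size is affected. It should be fixed because the safety conclusion cannot be reported unambiguously as the plan stands.

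**What to change.** Make the prior, the table and the operating characteristics one consistent set, by a dated clarification in Section 8.5:

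- **If the table is what was intended:** state the prior that generated it, and correct the stopping proportions to about 0.08% at p=2% and about 99.2% at p=25%.
- **If Beta(1.0, 5.0) was intended:** give the thresholds that follow from it (second row of the boundary table above), and re-issue the operating characteristics for that boundary.

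The authors must say which applies; the documents do not. In either case the final report should state which version was applied during the study and whether cumulative events reached either one at any point.

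The cost is a text or table correction in one section, two corrected cells or one simulation re-run, and one sentence in the report. No patients and no new data are needed.

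### Two cells of the section 8.5 operating-characteristics table do not match the printed boundary: 0.7% stopped at a 2% event rate should be about 0.08%, and 99.6% at 25% should be 99.2%.

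*Combined protocol and SAP*

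**What the plan says.** Section 8.5 sets thresholds on the number of subjects with a TRSAE. They run from 3 events at up to 9 subjects to 12 events at up to 78. The threshold column is headed "Stop if the number of subjects who have developed any of the TRSAE reaches", and the text adds that "we will start safety monitoring when 3 or more subjects have developed TRSAE".

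The performance check is then described. In each run "we generated a study with 78 independent Bernoulli trials", and the authors "compared the TRSAE outcomes with the above stopping boundary to determine whether the study was stopped". The number of runs is also given: "We repeated the simulation 100,000 times". For true rates of 2, 5, 10, 15, 20 and 25% the table reports:

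- studies stopped (the "proportion of stopped studies"): 0.7, 1.7, 21.8, 65.4, 92.8 and 99.6%;
- average subjects: 77.95, 76.93, 67.32, 46.97, 28.46 and 18.17;
- average subjects with a TRSAE: 1.55, 3.86, 6.73, 7.03, 5.70 and 4.55.

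From these results the section concludes that "we believe that our Bayesian stopping rule has satisfactory statistical properties".

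**The concern.** A boundary, a maximum sample size and a true event rate fix the stopping probability completely, so the table can be checked without simulation and without any outside figure. Two things look wrong.

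First, 0.7% at a 2% rate is too high for a rule that needs at least three events among the first nine subjects, or four among the first 16, and so on. Second, the 2% column disagrees with itself: an average of 77.95 out of 78 leaves almost no room for early stopping.

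This table is the only quantitative support that section 8.5 gives for the rule. The 2% cell is the false-stop rate when treatment is safe. The 25% cell carries the chance of failing to stop when the true rate is well above the 10% benchmark. Anyone citing these operating characteristics in a report would repeat the two figures.

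**Working it through.** **Inputs, all from section 8.5.** Maximum of 78 subjects; 100,000 runs; stop when the count reaches 3 (n ≤ 9), 4 (≤ 16), 5 (≤ 23), 6 (≤ 31), 7 (≤ 38), 8 (≤ 46), 9 (≤ 54), 10 (≤ 62), 11 (≤ 70) or 12 (≤ 78). The lowest threshold is 3, so starting to monitor at three events adds no further restriction.

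**Method.** Let f(n, s) be the probability of still being on study after n subjects with s events. For each new subject,

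f(n, s) = (1 − p)·f(n − 1, s) + p·f(n − 1, s − 1).

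Any mass at or above the threshold for n is moved to "stopped at n". The stopping probability is the total mass moved by n = 78. Average N and average events follow from the same recursion. The simulation standard error (SE) of a proportion P is √[P(1 − P)/100,000].

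**Results against the plan's figures.**

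| True rate | Stopped, plan | Stopped, exact | Gap in SE | Average N, plan | Average N, exact | Average events, plan | Average events, exact |
|---|---|---|---|---|---|---|---|
| 2% | 0.7% | 0.081% | +69 | 77.95 | 77.94 | 1.55 | 1.56 |
| 5% | 1.7% | 1.75% | −1.1 | 76.93 | 76.92 | 3.86 | 3.85 |
| 10% | 21.8% | 21.92% | −1.0 | 67.32 | 67.26 | 6.73 | 6.73 |
| 15% | 65.4% | 65.72% | −2.1 | 46.97 | 46.81 | 7.03 | 7.02 |
| 20% | 92.8% | 92.74% | +0.8 | 28.46 | 28.55 | 5.70 | 5.71 |
| 25% | 99.6% | 99.22% | +14 | 18.17 | 18.22 | 4.55 | 4.55 |

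The SE is about 0.009 percentage points at 2% and 0.028 at 25%. A separate simulation of 100,000 studies gave 0.085% and 99.24%. The four middle proportions and all six values of average N lie within about 2 SE, so the recursion describes the rule that was simulated. Only the two end proportions fall outside.

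**Hand check at 2%.** The chance of three or more events in the first nine subjects is

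1 − 0.98⁹ − 9(0.02)(0.98⁸) − 36(0.02²)(0.98⁷) = 1 − 0.83375 − 0.15314 − 0.01250 ≈ 0.0006, or 0.061% unrounded.

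That is about three quarters of the exact total of 0.081%. Later thresholds add little.

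**Consistency within the 2% column.** Average N = 78 − P(stop) × (78 − mean N at stopping). Exact mean N at stopping is 9.8, so each stopped study saves 78 − 9.8 = 68.2 subjects.

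- The printed average implies P(stop) = (78 − 77.95)/68.2 = 0.07%.
- A stopping probability of 0.7% would give an average N of 78 − 0.007 × 68.2 = 77.52, not 77.95.
- Taken together, the two printed figures need a mean N at stopping of 78 − 0.05/0.007 ≈ 71, which this boundary does not produce at a 2% rate.

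**Other readings tried.** None of these gives both end cells together with the rest of the table: a strict inequality on n; exceeding rather than reaching the threshold; a maximum of 39 subjects; and boundaries rebuilt from Beta(1, 5) and Beta(0.6, 5.4) priors at 90% and 95% cut-offs with different minimum counts. Beta(1, 5) at 90% without a three-event minimum does give 0.71% at 2%. It also gives 5.7% at 5%, 33.6% at 10% and an average N of 77.49 at 2%, so it did not generate this table.

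**The case against.** The strongest reply is that nothing of substance turns on these cells. The absolute gaps are 0.62 and 0.38 percentage points. Ratios such as ninefold at 2% (0.7/0.081) or a doubled miss rate at 25% (0.78% against 0.4%) compare very small probabilities. At 2% the printed figure makes the rule look worse than it is, so it does not flatter the design. The 5% to 20% columns, which carry most of the information, are sound. The rule leads only to serious consideration of stopping, and section 10.4 places the study in data analysis only from January 2017. All of this stands, and it keeps the point minor.

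The 2% cell also reads naturally as a dropped zero: 0.07% is about 1.2 SE below the exact value and agrees with the printed average N. A character lost when the PDF was read cannot be fully excluded for a single cell, though nothing shows it. The gap of 69 SE rules out chance as the explanation. It is not evidence of a faulty simulation.

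A reader might infer that the simulation failed, or that some other boundary was simulated. The documents do not support either: section 8.5 says the printed boundary was used, and both average rows agree with it in every column, including the two columns with the wrong proportions.

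A reader might also suppose that the corrected figures hold whatever is decided about the prior. They do not. The stated Beta(1, 5) prior with a 90% cut-off and a three-event minimum gives a different boundary from the one printed, starting with 3 events up to 13 subjects. That boundary would stop 0.23% of studies at 2% and 99.5% at 25%. This mismatch is a separate and larger question.

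**Conclusion.** Two stated operating characteristics are wrong for the boundary as printed. At a 2% rate the proportion stopped is 0.081% (0.1% to one decimal), not 0.7%. At 25% it is 99.22%, not 99.6%, so the chance of not stopping is 0.78% rather than 0.4%. Both are probably transcription slips.

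It would be going too far to read this as undermining the safety evidence. With the corrected values the rule still seldom stops a study well below the 10% benchmark and nearly always stops one at 25%.

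The result rests on the printed thresholds, a check after each subject, independent events with a constant rate, and a maximum of 78 subjects. These are the conditions section 8.5 describes, except that it does not state how often the count is checked. Checking only at the tabulated sample sizes gives the same stopping probabilities, because within each band the threshold is constant and the count cannot fall.

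**What to change.** Choose one of two corrections to the section 8.5 table:

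1. Change 0.7% to 0.08% (or 0.1% to one decimal) and 99.6% to 99.2%, and keep the table described as simulated. This costs two cells.
2. Replace the whole table with exact values for the printed boundary and describe it as exact. For rates of 2, 5, 10, 15, 20 and 25%:
   - stopped: 0.08, 1.7, 21.9, 65.7, 92.7 and 99.2%;
   - average subjects: 77.94, 76.92, 67.26, 46.81, 28.55 and 18.22;
   - average subjects with a TRSAE: 1.56, 3.85, 6.73, 7.02, 5.71 and 4.55.

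   The description of the simulation would then need rewording to match.

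Do not change only the two cells and label the table exact. The remaining 21.8, 65.4 and 92.8% are simulation estimates, and their exact values are 21.9, 65.7 and 92.7%.

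Neither option changes the design. If the boundary is altered, for example when it is reconciled with the stated prior, these figures lapse and every cell should be recomputed for the new boundary.
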